| Monitor | Clinical Trial Unit | Unit for clinical research, Västerbotten county council, SE-908 Umeå | |

4. Summary

| | |
|------------------------|---|
| Scientific title: | Visualization of Asymptomatic Atherosclerotic Disease for Optimum Cardiovascular Prevention: VIPVIZA – a Population-based RCT nested in Routine Care in Sweden |
| Principal Investigator | [name] |
| Study director | [name] |
| Study period | 2012-08-01–2026-12-31 |
| Hypotheses and aims | 
VIPVIZA has three distinct, but complementary hypotheses:
 
Pictorial representation of asymptomatic atherosclerotic disease, assessed with carotid ultrasound, has the potential to identify individuals at high risk of CVD with higher precision than conventional risk factor-based statistical models.
 
The clear understanding of an image of arterial disease during an early asymptomatic phase is of superior value in optimizing adherence to clinical preventive management for both physicians and patients. Literally, the English quotation is 'A picture speaks a thousand words'.
 
The resulting preventive management will improve control of premature CVD.
 
Specific aims
 
To assess the prevalence of asymptomatic atherosclerotic disease in men and women through identification of carotid plaques and measurement of CIMT, and to relate plaques and CIMT to clinically estimated CVD risk factors.
 
To assess the impact of visualization of atherosclerosis on quality of life, preventive measures, risk factor control and progress of atherosclerotic disease over the course of three years.
 
To explore the impact of visualization of atherosclerosis, as a low-intensive preventive intervention, on physicians' and patients' risk perception, communication and attitudes to CVD prevention.
 
To evaluate how individuals' health literacy and coping strategies relate to CVD risk at baseline, attitudes to screening, risk perception and preventive measures.
 
To investigate novel biomarkers in relation to CIMT and plaques at baseline, changes in conventional CVD risk markers and lifestyle, and progression of atherosclerosis.
 
To assess the impact of visualization of atherosclerosis by carotid ultrasound on premature CVD morbidity and mortality over the course of 5 and 10 years.
 |
| Primary outcome | SCORE and Framingham risk scores |

| | |
|---------------------|--|
| Secondary outcomes | CVD risk factors, lifestyle, ultrasound results (CIMT, presence of plaque, quantitative and qualitative plaque parameters, presence and degree of significant stenosis), prescriptions and purchases of medications (for the treatment of hypertension, dyslipidemia and diabetes), biochemical markers, and the clinical endpoints myocardial infarction, stroke, revascularization procedures and mortality (all-cause and CVD-specific). |
| Study design | A pragmatic randomized controlled trial nested within routine clinical care |
| Study population | Subjects aged 40, 50 or 60 years, invited as part of their VIP participation within Västerbotten primary healthcare. No:3700 |
| Follow-up period | 10 years from first ultrasound examination |
| Inclusion criteria | 
• age=40 years and first-degree relative with history of CVD at age <60 years• age=50 years and at least one of the following: first-degree relative with history of CVD at age <60 years, smoking, diabetes, hypertension, S-LDL cholesterol ≥ 4.5 mmol/L, abdominal obesity• age=60 years 
Individuals are included in the study only once, at whichever qualifying age point is achieved first.
 |
| Statistical methods | The differences in primary outcomes (SCORE risk and Framingham Risk Score) at one year between the treatment groups will be measured and analyzed using t-test. Differences in changes of SCORE and FRS from baseline to 1-year follow-up will be analyzed with regression methods to identify predictors of the changes in the scores. Survival curves will be established using Kaplan-Meier curves for CVD mortality and morbidity at 5 and 10 years of follow up comparing the intervention to the control group. Predictive Cox Proportional Hazard models will be developed to estimate the overall predictive ability of CIMT, plaque and risk factors on CVD morbidity and mortality at 5 and 10 years. Health economic modelling studies will be performed for evaluation of cost-effectiveness. Interviews with participants and physicians will be analyzed using qualitative content analysis. |
| Evaluation criteria | Primary and secondary outcomes will be evaluated according to Intention-to-treat methodology |

5. Background

5.1 Survey of the field and rationale for the trial

Primary prevention of cardiovascular disease (CVD) often fails due to the low precision of the conventional risk scores, and poor adherence among practitioners and patients to evidence-based prevention guidelines. Moreover, these risk scores focus on high-risk individuals only, despite 60-70% of all CVD events occurring among individuals at low or intermediate risk for CVD (1). VIPVIZA takes a different approach from current practice for the prevention of CVD. Instead of being based solely on indirect risk factors, this project evaluates the atherosclerotic disease itself while it still is silent, providing improved assessment, communication and perception of the CVD risk and higher motivation for prevention.

The evidence for effective modification of risk factors by lifestyle change and pharmacological treatment is well established. Despite this, suboptimal adherence to CVD prevention guidelines among practitioners and patients leads to poor risk factor control in both primary and secondary prevention (2-4). Contributory factors include poor communication about the CVD risk by the physician, inaccurate risk perception and lack of awareness of the weak association between the actual estimated and perceived CVD risk among patients (5, 6). The risk message is usually communicated verbally or numerically (7), while potentially more effective visual tools are seldom used. In addition to the format and framing of the message, the perceived risk also depends on social and cultural factors (8).

Moreover, for the success of risk management, the extent of the patient's behavioral change is crucially dependent on their psychological characteristics. The individual's ability to cope with stressful situations (coping strategy) (9), trust in their own capability to change behaviour (self-efficacy) (10), level of positive expectations in life (dispositional optimism) (11), and health literacy (capacity to understand health information and make appropriate related health decisions) (12) are important. Rational choices due to increased risk awareness often fail, and knowledge about a risk, on its own is rarely enough for sustainable behavioural change. These aspects are usually ignored in the field of primary prevention (13). For CVD prevention programs to be effective, a more person-centred approach towards the individual's clinical and behavioural change may need to be implemented (14), and in order to make use of existing evidence-based methods to the fullest extent, both the physicians' and individuals' adherence to existing CVD prevention guidelines should be targeted.

An alternative strategy to evaluate and improve CVD risk communication would be to directly view in pictorial form the degree of atherosclerotic disease before symptoms develop, rather than to indirectly evaluate risk factors of atherosclerosis (15-17). This is achieved with ultrasonography of medium sized arteries with assessment of carotid artery intima-media thickness (CIMT) and existing atherosclerotic plaques, which have a clearly higher predictive power for plaques. Pharmacological

and lifestyle interventions have the potential to slow down or even reverse the progress of ultrasound-assessed atherosclerosis (18, 19), but results on the contributory impact from image-based information on adherence to prevention are inconsistent (20, 21).

Therefore, large-scale randomized controlled trials (RCTs) targeting low and intermediate-risk adults with a focus on assessing the impact of viewing an image of existing silent disease on the stratification and communication of CVD risk to physicians and patients, as well as on major clinical outcomes, should be prioritized (1, 2, 21).

[figure not shown]
5.2 Hypotheses

VIPVIZA has three distinct, but complementary hypotheses:

- Direct viewing of a pictorial representation of asymptomatic atherosclerotic disease, assessed with carotid ultrasound, has the potential to identify individuals at high risk of CVD with higher precision than conventional risk factor-based statistical models.
- The clear understanding of an image of arterial disease during an early asymptomatic phase is of superior value in optimizing adherence to clinical preventive management for both physicians and patients: "A picture speaks a thousand words".
- The resulting preventive management will improve the control of premature CVD.

5.3 Theoretical model

Social, genetic, psychological and behavioral mechanisms impact the subclinical molecular processes that manifest as clinical risk factors and the subclinical morphologic atherosclerotic process, and eventually in clinical cardiovascular disease events or death.

6. Objective and aims

6.1 Objective

To assess the impact of a visual image and pictorial report, seen and discussed by both physician and patient, for improving guideline adherence and patient perception and understanding of the CVD risk and consequent motivation for prevention. The extent of the impact is assessed by differences between randomization groups in Framingham Risk Score and SCORE as well as changes in these scores after one and three years. Differences between groups will also be evaluated by risk factor assessment and a further scan after three years to determine disease progression, and a comparison of the prevalence of acute events and mortality at five and 10 years.

6.2 Specific aims

1. To assess the prevalence of asymptomatic atherosclerotic disease in men and women through identification of carotid plaques and measurement of CIMT, and to relate plaques and CIMT to clinically estimated CVD risk factors.
2. To assess the impact of pictorial representations of atherosclerosis on quality of life, preventive measures, risk factor control and progress of atherosclerotic disease over the course of three years.
3. To explore the impact of pictorial representations of atherosclerosis, as a low-intensive preventive intervention, on physicians' and patients' risk perception, communication and attitudes to CVD prevention.
4. To evaluate how individuals' health literacy and coping strategies relate to CVD risk at baseline, attitudes to screening, risk perception and preventive measures.
5. To investigate biomarkers in relation to CIMT and plaques at baseline, changes in conventional CVD risk markers and lifestyle, and progression of atherosclerosis.
6. To assess the impact of the pictorial representation of atherosclerosis by carotid ultrasound on premature CVD morbidity and mortality over the course of 5 and 10 years.

7. Endpoints

7.1 Primary endpoints:

- 7.1.1 SCORE (22)
- 7.1.2 Framingham risk score (23)

7.2 Secondary endpoints

- 7.2.1 CVD risk factors (blood pressure, serum cholesterol, LDL, HDL, triglycerides, fasting glucose, HbA1c)
- 7.2.2 Lifestyle (physical activity, tobacco use, alcohol use, eating habits)
- 7.2.3 Ultrasound results (CIMT, presence of plaque, quantitative and qualitative plaque parameters, presence and degree of significant stenosis)
- 7.2.4 Pharmacological treatments of hypertension, dyslipidemia and diabetes, prescriptions and purchases
- 7.2.5 Biochemical biomarkers
- 7.2.6 Clinical endpoints: Hospitalizations due to CVD, diagnostic and therapeutic revascularization procedures (PTCA, PCI, stent) regarding atherosclerotic disease and deaths (all-cause and CVD-specific), as specified in Appendix 2: VIPVIZA diagnoses clinical events and causes of deaths
- 7.2.7 Quality of life.

[figure not shown]
8 Project description

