Medical Biobank, Umeå University Hospital. Written information about ultrasound results are sent to all SPs and their respective family physicians in primary care.

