11.8 Registry data

11.8.1 Pharmacological treatment: At baseline, 1 and 3 years: Prescriptions retrieved from medical records in the Västerbotten County Council digital system registries. At 1 and 3 years: purchases of pharmacological products from the Statistics on Pharmaceuticals at the National Board of Health and Welfare.

11.8.2 Socio-economic status: Income and highest attained educational level from Statistics Sweden.

11.8.3 Cognitive characteristics at age 18 (males only): The Conscripts register at the National Archives Database.

11.8.4 Clinical events: From data retrieved from registers at the National Board of Health and Welfare at 5 and 10 years after the last ultrasound examination: Hospitalizations due to cardiovascular morbidity and diagnostic and therapeutic procedures and mortality (all-cause and CVD-specific), according to the International Classification of Diagnoses ICD10, as specified in Appendix 2 VIPVIZA diagnoses clinical events.

12 Intervention and control

12.1 Randomization and invitations to visit.

VIP participants who are eligible for participation in VIPVIZA are given written and verbal information about the VIPVIZA study and are invited to the study at the occasion of their participation in VIP at their primary health care centre. The district nurses who conduct the health dialogues also sign that the study information is given and collect the informed consent forms and send them to research nurses at KFC. The research nurses register all forms.

SPs are then randomized to two equal groups (intervention and control group) before the first ultrasound examination. The randomization list is generated prior to the study through simulation from a uniform probability distribution. At this stage a unique identification code is assigned to each SP. Invitation with appointment times for the baseline visit is sent by mail to both groups by the research nurses who manage the study at KFC.

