12.2 Intervention group

12.2.1 Procedures

- Baseline: Research nurses send invitation letters with an appointment time for the baseline ultrasound examination by mail to those who gave informed consent to participation in VIPVIZA. One reminder letter with a new appointment time is sent to non-attenders. At this visit, participants answer the psychometric questionnaires and undergo the baseline ultrasound examination. Ultrasound examinations are performed by sonographers specifically trained in carotid ultrasound techniques (Biomedical Scientists) from the Department of Clinical Physiology, Heart Centre, Umeå University Hospital. Examinations are undertaken in hospitals in three towns in Västerbotten county (Umeå, Skellefteå and Lycksele), and at the local primary healthcare centres in rural areas. A portable automatic carotid ultrasound equipment (CardioHealth Station®, Panasonic Healthcare Corporation of North America, Newark, NJ, USA) is used. A standardized protocol according to current guidelines is applied for the examinations (46, 47). The angle of insonation is automatically provided by the system and is recorded. Measurements of CIMT (max, min and mean values)

are automatically obtained (41). The same ultrasound machine is used during the entire study period.

Within two weeks of the ultrasound examination, information about the carotid ultrasound results are sent by post to the participant, see 12.2.2. At the same time, exactly the same information is sent to their respective primary care physician. After an additional 2-4 weeks participants receive a follow-up phone call by a research nurse in order to ascertain whether the information was accurately understood and to reassure the participant and give additional information if needed.

- Qualitative interviews with a subgroup of around 20 SPs within the intervention group concerning their experiences and reactions to the information about the ultrasound results.
- Qualitative interviews with General Practitioners who have received at least five written reports from VIPVIZA regarding their patients.
- At 6 months, participants receive a reminder in the form of a letter with the identical information about the ultrasound results and very brief reminder about possible preventive measures.
- At 9 months, participants receive a letter with information about proceedings in the study and reminder about the 1-year follow-up.

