12.3 Control group procedures

- Baseline: Identical to procedures for the intervention group, except that no information about ultrasound results are sent to SPs and their respective GPs, and there are no qualitative interviews.
- At 1-year: Identical to follow-up procedure for the intervention group, except that there is no sub-study regarding perceptions about the baseline ultrasound report.
- At 3-years: Identical to follow-up procedures for the intervention group, except that there are no questions regarding perceptions about the baseline ultrasound report and the phone call and no qualitative interviews.

13 Statistical analyses and considerations

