13.2.3 Summary of planned analyses

The differences in primary outcomes (SCORE risk and Framingham Risk Score) at one year between the treatment groups will be measured and analysed using t-test, for a detailed statistical analyses plan see Appendix 4. As the group sizes are large (more than thousand), it is valid to assume normal distribution of the error around the mean value estimates in both the intervention and the control group. A two-sided p-value <0.05 will be regarded as statistically significant. Complementary to the absolute difference in the Score and the statistical testing of hypotheses, Cohen's effect size will be derived for the difference in mean outcome values divided by a pooled standard deviation of the Score between the 2 groups.

In sensitivity analyses, we will conduct a linear regression covariate-adjusted analysis. We will use the continuous form of the primary outcomes (SCORE risk and Framingham Risk Score) as outcome in the

regression analysis. We will assess the effects of the intervention independently for each of the outcome measures. As many of the baseline co-variates (including sex and age) are related to the prognosis of outcomes, adjustment of pre-defined covariates in the regression analysis might yield in adjusted coefficients which are slightly further from 1.

We will also analyze the changes of SCORE and FRS from baseline to 1-year follow-up and use regression methods to identify predictors of the changes in the scores.

Since patients are recruited into the study during three years from mid-2013 to mid-2016, any change in physicians' prescribing behaviour over the course of the study will be evaluated by comparing prescriptions issued for lipid-lowering and anti-hypertensive medication to participants recruited during the first, second and third years.

Similar statistical methods will be applied for evaluation of the three-year results. At that time point also changes in plaque distributions and IMT variables including differences between intervention and control group will be evaluated.

In long-term, adding risk communication using visualisation of carotid ultrasound results will be compared to routine CVD risk assessment and control within the primary health care setting in hospitalisation due to stroke, myocardial infarctions and revascularisations (at 5-year and 10-year) and reducing overall mortality and cause-specific mortality due to myocardial infarctions and stroke (at 5-year and 10-year) compared to.

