Simple survival curves will be established using Kaplan-Meier curves for CVD mortality and morbidity at 5 and 10 years of follow up comparing the intervention to the control group. Thereafter, predictive Cox Proportional Hazard models will be developed to estimate the overall predictive ability of CIMT, plaque and risk factors on CVD morbidity and mortality at 5 and 10 years in the control group and in the intervention group, taking into account time at risk for disease and deaths. Receiver Operating Characteristic Curves (ROC) will be calculated by estimating the Area Under the Curve (AUC) to ensure the highest possible sensitivity and specificity of the predictions. Confirmatory and exploratory statistical modelling will establish relationships between the intervention and intermediate and mediating factors and variables' relative contribution to explain changes in the outcome variables.

Since participants are recruited into the study during the three years from mid-2013 to mid-2016, any change in physicians' prescribing behaviour over the course of the study will be evaluated by comparing prescriptions issued for lipid-lowering and anti-hypertensive medications among participants recruited during the first, second and third years.

As a basis for how to build regression models Causal diagrams (directed acyclic graphs - DAGs) will be established and causal mediation analysis will be undertaken to illustrate the impact of social, gender, psychological and environmental factors by biomedical risk indices on CVD morbidity and mortality.

Health economic modelling studies will be performed for evaluation of cost-effectiveness. Interviews with participants and physicians will be transcribed verbatim and analyzed using Qualitative Content Analysis (52).

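### Diagnostic procedures enter some definitions of the clinical endpoint but not others, and open disclosure of scans may raise procedure counts by arm, mainly at 5 years

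*Protocol*

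**What the plan says.** The protocol describes the clinical endpoint in several places.

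- **7.2.6** lists CVD hospitalisations, then "diagnostic and therapeutic revascularization procedures (PTCA, PCI, stent) regarding atherosclerotic disease and deaths (all-cause and CVD-specific", with details left to Appendix 2.
- **11.8.4** retrieves from the registers "Hospitalizations due to cardiovascular morbidity and diagnostic and therapeutic procedures and mortality (all-cause and CVD-specific". Procedures are not limited there to revascularisation.
- **Section 4, Summary (secondary outcomes)** names "the clinical endpoints myocardial infarction, stroke, revascularization procedures and mortality (all-cause and CVD-specific", with no diagnostic procedures.
- **6.1** frames the 5- and 10-year comparison around acute events and death.
- **13.2.3** compares the arms on "hospitalisation due to stroke, myocardial infarctions and revascularisations (at 5-year and 10-year" and on overall and cause-specific mortality. It then adds: "Simple survival curves will be established using Kaplan-Meier curves for CVD mortality and morbidity at 5 and 10 years of follow up", by arm, without saying what counts as morbidity.

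On disclosure, 12.2.1 has the scan report posted to the intervention participant within two weeks, and "exactly the same information is sent to their respective primary care physician". In the control arm, 12.3 makes the baseline procedures the same, "except that no information about ultrasound results are sent to SPs and their respective GPs". From the three-year visit (9.2.4) the difference ends: "Written information about ultrasound results are sent to all SPs and their respective family physicians in primary care". The SAP amendment accepts that from then on the arms are no longer parallel.

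**The concern.** Hypothesis 3 and aim 6 ask whether disclosure improves control of premature CVD. An infarction, a stroke or a death reaches the registers largely whatever the physician knew beforehand. A diagnostic procedure or an elective revascularisation depends on someone deciding to investigate or treat, and for three years that decision is made with the scan report in one arm and without it in the other. Section 15.1 expects the report to change physicians' behaviour, and the SAP's reference list gives the trial's main report as open-label.

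If such procedures count as morbidity, the informed arm can gain events that reflect closer looking rather than more disease. That pushes the ratio upwards and can hide part of a real benefit. Separately, an analyst working from 7.2.6 and 11.8.4 would count events that one working from the Summary, 6.1 or 13.2.3 would leave out.

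**Working it through.** **Step 1: the definitions side by side**

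| Place in protocol | Diagnostic procedures | Revascularisation |
|---|---|---|
| Summary | not named | named |
| 6.1 | not named | not named |
| 7.2.6 | named | named |
| 11.8.4 | named | covered by therapeutic procedures |
| 13.2.3, arm comparison | not named | named |
| 13.2.3, Kaplan-Meier | components not listed | components not listed |

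The inconsistency needs no assumed figure.

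**Step 2: possible size**

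The plan has no figure to reproduce. The sizing table in 13.1 covers risk factors, risk scores and CIMT, not clinical events. The only input from the documents is the period of unequal disclosure, D = 3 years. The rest is assumed:

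- s, the share of control-arm events that are procedures only: 2/9 to 4/9 (22-44%). Examples are 7% hard events with 2% procedures, and 5% with 4%.
- u, the relative rise in procedures caused by disclosure: 0.30 to 0.50, in years 0-3 only.
- constant rates, with the two kinds of event adding up.

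With no true effect, ratio(T) = 1 + s × u × D/T.

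- 5 years: 1 + 0.222 × 0.30 × 0.6 = 1.04, up to 1 + 0.444 × 0.50 × 0.6 = 1.13.
- 10 years: 1 + 0.222 × 0.30 × 0.3 = 1.02, up to 1 + 0.444 × 0.50 × 0.3 = 1.07.

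**Step 3: controls catch up.** Suppose controls show the same rise for up to three years after their own disclosure at year 3.

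- 5 years (two catch-up years): (1 + 0.6su)/(1 + 0.4su), which is 1.040/1.027 = 1.01 up to 1.133/1.089 = 1.04.
- 10 years (three catch-up years): numerator and denominator are equal, so 1.00.

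**Step 4: a true benefit.** Take s = 1/3, u = 0.30 and a true 10% cut in hard events, so that the hard-event ratio is 0.90.

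- 5 years: 0.667 × 0.90 + 0.333 × 1.18 = 0.99.
- 10 years: 0.667 × 0.90 + 0.333 × 1.09 = 0.96.
- If prevention also cuts procedures by 10%: 0.600 + 0.393 × 0.90 = 0.95 and 0.600 + 0.363 × 0.90 = 0.93.

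**Step 5: wider assumptions.** With s from 20% to 60% and u from 25% to 100%:

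- No true effect: 1.03-1.36 at 5 years and 1.015-1.18 at 10 years.
- True ratio of 0.80 on both kinds of event: these values times 0.80, so 0.82-1.09 and 0.81-0.94.

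**Time origin.** T runs from the baseline scan, as the Summary's follow-up period does. Section 11.8.4 counts from the last ultrasound examination. If that means the three-year scan, the 5-year comparison has T = 8 and the Step 2 range becomes 1 + 0.222 × 0.30 × 3/8 = 1.025 to 1 + 0.444 × 0.50 × 3/8 = 1.083.

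**The case against.** The case for leaving the endpoint alone has real force.

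- **No composite is written out.** 7.2.6 is a list. 13.2.3, which sets the arm comparison, names no diagnostic procedures, and the examples bracketed in 7.2.6 are all therapeutic. A reader might infer that the plan counts diagnostic procedures as CVD morbidity. The documents do not go so far: they leave the term undefined. This point stands.
- **Appendices 2 and 4 are not among the documents available.** They hold the event definitions and the detailed analysis plan, and may settle the matter. The SAP amendment at hand covers only 6-year risk scores, risk factors and ultrasound. This stands too, but the disagreement among the protocol's own sections remains.
- **The mechanism is not documented.** Section 15.1 says mild to moderate disease has no specific treatment beyond risk factor control, and expects better adherence to prevention guidelines rather than more investigation. Its remark on rapid referral is not specific to one arm. Stenosis above 50% is disclosed, referred and excluded in both arms. So the rise in procedures is possible, not shown. The stenosis rule concerns the carotids only, however, and participants told of lesser plaque stay in the trial.
- **Unequal disclosure lasts three years.** Later scans are reported in both arms, so they add no clear arm difference. This limits the bias, especially at 10 years.

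A reader might also infer that a real benefit could be cancelled or reversed at 10 years. That follows only if the uplift runs for the whole decade: with 6% hard events cut to 5.4%, and 3% procedures raised by 30%, (5.4 + 3.9)/9 = 1.03. Confined to years 0-3, the same case gives 0.96.

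**Conclusion.** The concern holds in a limited form. The protocol's sections disagree on whether diagnostic procedures belong to the clinical endpoint, and the morbidity comparison by arm does not say what it contains. Open disclosure to one arm for three years gives a plausible route by which procedure counts could differ for reasons other than disease.

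On the main assumptions (22-44% of events, 30-50% rise, years 0-3), the inflation under no true effect is about 4-13% at 5 years and 2-7% at 10 years, falling to 1-4% and to nothing with full catch-up. A modest true benefit could be nearly masked at 5 years (0.99 in place of 0.90) and would be partly diluted at 10. Reversal appears only at 5 years and towards the extreme of the wider assumptions.

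Every one of these sizes rests on assumed rates. The endpoint is secondary, and the primary endpoints, SCORE and Framingham, are unaffected. The documents do not support a claim that revascularisation must be dropped: it is named in the Summary, 7.2.6 and 13.2.3, and keeping it is a defensible choice.

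**What to change.** 1. Exclude diagnostic procedures from the between-arm CVD morbidity endpoint, and report them by arm as process outcomes.
2. Add a between-arm comparison at 5 and 10 years of first myocardial infarction, stroke or CVD death, with all-cause death alongside.
3. Keep revascularisation as a separately reported component, distinguishing elective procedures from those tied to an acute event where the register allows.
4. List the components of the Kaplan-Meier morbidity curves. Reconcile the Summary, 6.1, 7.2.6, 11.8.4 and 13.2.3, and check them against Appendix 2.

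The register data are already to be retrieved, so the work is mainly wording and analysis specification. The price is precision in the hard-event comparison. If procedures are 22-44% of events, 7/9 to 5/9 of events remain, and the interval on the log scale widens by a factor of about 1/√(7/9) = 1.13 to 1/√(5/9) = 1.34.
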